5. EFFICACY ANALYSIS

5.1. Analysis of the Primary Efficacy Endpoint

The primary efficacy variable, subject ranks based on the combined assessment of function and survival (CAFS) after 24 weeks of treatment will be performed using an analysis of covariance model (ANCOVA) following multiple imputation. The estimand framework described in Section 3.3.1 will be used. The ANCOVA model will contain the following main effects: treatment (PTC857 or placebo), the amount of change in the subject's ALSFRS-R score during the Screening Period (<1, 1-2, or 3-4-points total loss), TRICALS risk profile (continuous), use of Approved Background Therapy for ALS (Yes [either riluzole, edaravone, or sodium phenylbutyrate/taurursodiol], No). Baseline ALSFRS-R score (continuous) and The TRICALS risk profile (continuous) will be included as covariates.

Subjects who discontinue from the study prior to week 24 will have their week 24 ALSFRS-R score imputed using the same datasets described in Section 5.5.1.2. In each of the 100 imputed datasets, subjects who die will have their death day (study day) incorporated as part of the combined assessment of function and survival.

The p-value for the treatment comparison (PTC857 versus Placebo) at week 24, estimate of LSMEANS for the treatment differences (PTC857 – Placebo), and the two-sided 95% confidence interval of the LSMEANS difference will be presented for the ITT1 analysis set (obtained from PROC MIANALYZE in SAS). If the p-value for the treatment arm comparisons at week 24 is less than 0.05, then the study will be declared as positive.

This analysis will also be repeated for the ITT2 analysis set and a nominal p-value for treatment arm comparison at week 24 presented.

In addition, averaged win probability (Rubin's rule) and a win-odds, will also be presented.

$$\label{eq:winprobability} Win\ probability(\theta) = 0.5 + \frac{\bar{R}_i - \bar{R}_j}{N_i + N_j} & Where: \\ \bar{R}_i = \ mean\ ranks\ for\ treatment\ groups_{i,j} \\ N_i = \ No.\ subjects\ in\ treatment\ groups_{i,j} \\ \end{cases}$$

$$Win\ odds = \frac{\theta}{(1-\theta)}$$

Given the difficulties in interpreting and quantifying the treatment effect from the CAFS analysis, results from the MMRM analysis in ALSFRS at week 24 (Section 5.5) will be used to describe the treatment effect in terms of loss of function). Similarly, survival differences will be described using results from the Survival analysis (Section 5.7)

5.2. Sensitivity Analysis – Unstratified Analysis

The primary efficacy analysis described in Section 5.1 will be repeated without including the two stratification factors (change in ALSFRS-R score during the 8-week Screening Period and standard of care therapy for ALS).

5.3. Sensitivity Analysis – Actual Stratification

A sensitivity analysis to determine the effect of any incorrect stratification during randomization on the primary analysis will also be performed. The primary analysis (Section 5.1) will be

repeated using the actual stratification, defined as the stratification level they should have been randomized from.

5.4. Per protocol Analysis Set

The primary efficacy analysis described in Section 5.1 will be repeated using the Per protocol analysis set described in Section 2.4. For this analysis the seed to be used in the MI model is 587432

5.5. Analysis of Secondary Efficacy Endpoints

For all efficacy analyses described in this Section and in Sections 5.6 through 5.8, partially stratified analysis (excluding either one of the two stratification factors) or fully unstratified analyses (exclusion of both factors) may be considered should there be issues with statistical modeling arising from sparse strata.

5.5.1. Change from Baseline in ALSFRS-R

5.5.1.1. Mixed Model Repeated Measures (MMRM)

Change from baseline in ALSFRS-R at Week 24 will be evaluated by means of a mixed model repeated measures analysis using all available ALSFRS-R scores up to Week 24. The estimand framework described in Section 3.3.2 will be used. The model will include fixed categorical effects of treatment (PTC857 or placebo), use of approved background therapy for ALS (Yes vs No), the amount of change in the subject's ALSFRS-R score during the Screening Period (<1, 1-2 or 3-4 points total loss), time of collection (nominal week at the visit as a categorical variable), as well as the continuous, fixed covariates of baseline ALSFRS-R, and The TRICALS risk profile. In addition, the following interaction terms will be included: Time by treatment, time by baseline ALSFRS-R, and TRICALS risk profile by time. Subject will be included as a random effect. The Restricted Maximum Likelihood (REML) estimation approach will be used with the variance-covariance structure set as unstructured (UN). Other types of covariance matrices will be explored in the case of non-convergence of the UN. Subjects with no post baseline results for the outcome variable will be excluded. This analysis will be performed for both the ITT1 and ITT2 analysis sets.

Observed and change-from-baseline values will also be summarized descriptively at each visit.

In supplementary analyses, score changes from baseline at Week 24 for the ALSFRS-R subdomains will be analyzed under the same estimand framework where MMRM models will be used to implicitly impute missing data. Nominal P-values for the treatment arm comparison, estimate of LSMEANS for the treatment differences (PTC857 – Placebo) at Week 24, and the two-sided 95% confidence intervals of the LSMEANS difference will be presented.

5.5.1.2. Analysis of Covariance Model (ANCOVA) with Multiple Imputation:

An additional analysis to evaluate change from baseline in ALSFRS-R will be performed using an analysis of covariance model (ANCOVA) following multiple imputation (MAR assumption). Missing ALSFRS-R scores, (including those missing due to death) will be imputed using multiple imputation (MI), 100 imputations will be generated using PROC MI in SAS. The Fully Conditional Specification (FCS) model using the regression method will be used.

The ANCOVA model will contain the change from baseline in ALSFRS-R as the response variable and will include the following main effects: Treatment group (PTC857, or Placebo), the amount of change in the subject's ALSFRS-R score during the Screening Period (<1 point, 1-2-points or 3-4-points total loss), use of approved background therapy for ALS (Yes vs No). Baseline ALSFRS-R score (continuous) and The TRICALS Risk Profile (continuous) will be included as covariates.

The seed to be used in the MI model is 20221219.

For each imputed complete data set, the change from baseline in ALSFRS will be analyzed at week 24 using the ANCOVA analysis model.

The 100 estimates and standard errors will then be combined using Rubin's rule to produce a single estimate with standard error, confidence interval and nominal p-value using the PROC MIANALYZE procedure in SAS.

5.5.1.3. Pattern Mixture Model - Missing not at random assumption:

A sensitivity analysis for the primary efficacy endpoint, ALSFRS-R score change from baseline at Week 24, will handle missing efficacy data using the assumption that data are missing not at random using a control-based Pattern-Mixture Model (PMM). This method will assume that participants who discontinue from study treatment early will have an ALSFRS-R score that is similar to participants on placebo. For the PMM model, 100 imputations will be generated using PROC MI of SAS. The seed to be used for this analysis will be 1001.

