1.1. Study Design

Brief description of the Study Design

This is a Phase 2, randomized, double-blind, placebo-controlled, parallel-group study to assess the effects of PTC857 (also known as utreloxastat) in adult male and female subjects diagnosed with ALS. Eligible male and female subjects aged between 18 and 80 years will be enrolled in this study. The study consists of 5 periods: Screening, Treatment (Part A), LTE (Part B), Continued LTE (Part C), and Follow Up as illustrated in Figure 1 below.

Approximately 340 subjects who meet the inclusion and exclusion criteria will be randomized in a 2:1 ratio to receive PTC857 (250 mg BID) or matching placebo with 2 stratification factors:

- 1. Amount of change in ALSFRS-R score during the 8-week Screening Period by points total loss:
 - a. <1,
 - b. 1-2,
 - c. 3-4, or
 - d. >4 points total loss
- 2. Use of edaravone, sodium phenylbutyrate/taurursodiol, or neither for the treatment of ALS at Screening as standard-of-care therapy:
 - e. Edaravone
 - f. Sodium phenylbutyrate/taurursodiol
 - g. Neither edaravone nor sodium phenylbutyrate/taurursodiol

[figure not shown]
Before protocol amendment version 4.0, dated 31 OCTOBER 2022, the second stratification factor above (treatment for ALS at baseline) was based on use of riluzole alone (with two levels: on riluzole and not on riluzole). Protocol amendment 4.0 opened the study to allow for

randomization of subjects who were taking other treatments for ALS, if approved in their region of participation, specifically edaravone or sodium phenylbutyrate/taurursodiol if their treatment was considered stable. In protocol amendment 4.0, the original riluzole stratification groups (on riluzole vs. not on riluzole) would be amalgamated, and randomization would be based on edaravone, sodium phenylbutyrate/taurursodiol, and Neither treatment status, as indicated above.

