4.2. Demographics and Baseline Characteristics

Subjects' demographics and baseline characteristics will be summarized overall and by treatment group for the ITT1, ITT2, and Safety analysis sets.

Continuous variables (e.g., age and weight) will be summarized using descriptive statistics (n, mean, standard deviation, median, minimum, and maximum). Qualitative variables (e.g., sex, race, and ethnicity) will be summarized with counts and percentages.

The demographic parameters will include age category (<65 and ≥65 years), gender, race, and ethnicity. Age will also be summarized as a continuous variable. The baseline parameters include, height, body weight, BMI, ALSFRS-R score, amount of change in ALSFRS-R score during the screening period (<1, 1-2, 3-4, or >4 points total loss) use of standard of care (SoC) medications for ALS at baseline, and disease characteristics at screening.

By-subject listings of demographic and other baseline characteristics will be provided for all randomized subjects. These listings will use flag variables to identify subjects in various analysis sets (ITT1, ITT2, safety and per-protocol).

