5.5.2. Analysis of Other Continuous Secondary Endpoints

The following secondary (continuous) endpoints will be analyzed for both the ITT1 and ITT2 analysis sets under the estimand framework described in Section 3.3.2, where an MMRM is used to implicitly impute missing data. The MMRM models will include fixed categorical effects of treatment (PTC857 or placebo), use of approved background therapy for ALS (Yes vs No), the amount of change in the subject's ALSFRS-R score during the Screening Period (<1, 1-2 or 3-4 points total loss), time of collection (nominal week at the visit as a categorical variable), as well as the continuous, fixed covariates of baseline endpoint variable (e.g., ALSFRS-R, ALSAQ-40), and The TRICALS risk profile. In addition, the following interaction terms will be included: Time by treatment, time by baseline value of endpoint, and TRICALS risk profile by time.

P-values for the treatment arm comparison at week 24, estimate of LSMEANS for the treatment differences (PTC857 – Placebo), and the two-sided 95% confidence intervals of the LSMEANS difference will be presented:

- Change from baseline in ALSFRS-R in the Intent-to-Treat 2 (ITT2) Analysis Set after 24 weeks of treatment.
- Quality of life as assessed by Amyotrophic Lateral Sclerosis Assessment Questionnaire (ALSAQ-40) after 24 weeks of treatment, for ITT1 and ITT2 analysis sets.
- Change from baseline in Modified Norris Scale total score, limbs score and bulbar score at Week 24, for ITT1 and ITT2 analysis sets.

• Change from baseline in slow vital capacity (SVC) as assessed by pulmonary function tests (PFTs) after 24 weeks of treatment for the ITT1 and ITT2 analysis sets.

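### Screening-decline factor: SAP 5.1 and 4.6 disagree on the status of ITT2 CAFS, the 5.6 subgroups overlap, the NfL model omits the factor, and the >4 level is unnamed in the ITT2 models

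*SAP*

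**What the plan says.** **Strata and sets.** SAP 1.1 stratifies randomization on screening loss in four levels, the last being "d. >4 points total loss". The baseline table in 4.2 also uses four: "amount of change in ALSFRS-R score during the screening period (<1, 1-2, 3-4, or >4 points total loss". By 2.2, ITT1 is the dosed, randomized subjects who lost 4 points or fewer, and ITT2 is the same without that limit.

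**Models.**
- CAFS ANCOVA (5.1): "Screening Period (<1, 1-2, or 3-4-points total loss", then "This analysis will also be repeated for the ITT2 analysis set and a nominal p-value for treatment arm comparison at week 24 presented".
- ALSFRS-R MMRM (5.5.1.1): "ALSFRS-R score during the Screening Period (<1, 1-2 or 3-4 points total loss", then "This analysis will be performed for both the ITT1 and ITT2 analysis sets".
- ANCOVA after multiple imputation (5.5.1.2): "<1 point, 1-2-points or 3-4-points total loss".
- Other continuous secondary endpoints (5.5.2): the same three levels, for endpoints that "will be analyzed for both the ITT1 and ITT2 analysis sets".
- Cox model (5.7): stratified on the same three levels. Section 3.3.3 extends the survival estimand to ITT2.
- Plasma NfL MMRM (end of 5.5.2): no screening-decline factor.
- Part B/C SAP 5.2.1 and 5.4: three levels again, with 5.2 applying the efficacy analyses to both sets.

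**Testing sequence (4.6).** After the primary come ALSFRS-R in ITT1 (step 1), ALSFRS-R in ITT2 (2), CAFS in ITT2 (3), ALSAQ-40 in ITT1 (4) and log NfL in ITT1 (5). Each is tested at two-sided 0.05, and testing stops at the first failure.

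**Subgroups (5.6).** Screening decline appears as 1-2, 2-4, 1-4, and for ITT2 as <4 versus >4.

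The erratum of 29 October 2024 corrects only the TRICALS wording in 5.1.

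**The concern.** Steps 2 and 3 are the formal tests of the secondary objective in SAP 1.2.2 that covers patients whatever their rate of decline before baseline. They differ from step 1 and the primary only through the >4 subjects, and the model text never gives those subjects a level.

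The status of step 3 matters because it gates ALSAQ-40 and NfL. If its p-value is nominal, a reader can ask whether a failure at step 3 stops the sequence.

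The subgroup categories as listed cannot form one factor. The NfL model departs from the other MMRMs on a factor used to randomize, with no reason given.

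**Working it through.** **1. The plan's own figures.** Inputs from SAP 1.5: 205 and 102 subjects, difference 2 points, SD 5.3, survival 96.5% and 95%. A simulated joint rank test (20,000 runs) gives 85.8% power, against the stated 85% or so. The protocol's 2.5 points, which the SAP calls a typographical error, gives 95.7%. For the randomized number, 307/0.9 = 341.1, rounded up to 342, against about 340.

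**2. Size of the >4 group.** 340 - 307 = 33, and 33/340 = 9.7%. This is an upper figure, because undosed subjects are in neither set. At 2:1 it is 22 and 11. Expected deaths at the planned rates: 22 × 0.035 + 11 × 0.05 = 0.77 + 0.55 = 1.3, spread over two background-therapy strata.

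**3. 5.1 against 4.6.** One section presents the ITT2 CAFS p-value as nominal; the other gives it 0.05 and a place in the sequence. In the simulation described in item 6, with four levels, step 3 fails in 0.7-3.7% of trials where the primary and steps 1 and 2 pass. Those are the trials in which the wording could be disputed.

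**4. Subgroups.** A loss of 2 points falls in 1-2, 2-4 and 1-4. A loss of 3 falls in 2-4 and 1-4. A loss of 0 falls in none. The categories are neither exclusive nor exhaustive.

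**5. NfL model.** Adding the factor costs 3 - 1 = 2 parameters in ITT1 and 4 - 1 = 3 in ITT2.

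**6. What literal three-level coding would do.** If >4 were set to missing, the ITT2 MMRM would use the ITT1 subjects. In 9,000 simulated trials (single-visit ANCOVA in place of the MMRM), step 1 and step 2 p-values were then identical. The identity needs the stratum used to agree with the actual loss. Step 3 would not exactly repeat the primary: decisions agreed in 99.2-99.6% of trials.

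How often this would change step 2 depends on the effect in >4 subjects, which the documents do not give. A second simulation (4,000 trials per scenario) took effect, SD, survival and ITT1 size from SAP 1.5. Assumed: ITT1 level means of -4, -6 and -8 in equal thirds, a >4 mean lower by a further 2 or 6 points, no baseline or TRICALS covariates, and a Week 24 ANCOVA in survivors. The primary and step 1 both passed in 81% of trials.

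| Assumed effect in >4 | >4 dropped: step 2 differs from four-level result | >4 pooled with 3-4: step 2 differs |
|---|---|---|
| +2 | 0.7-1.0% | 0.1-0.5% |
| 0 | 4.1-4.4% | 0.4-2.1% |
| -2 | 11.4-11.6% | 1.6-6.1% |

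Percentages are of all trials, counting only those that pass the primary and step 1. With four levels coded, the difference is zero.

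**The case against.** **The >4 subjects are plainly meant to stay.** The ITT2 definition includes them, 4.2 tabulates them, and 5.6 has an ITT2 subgroup that needs them. Section 5.5.1.1 uses all available scores and names one exclusion only: no post-baseline result. The sample code in Appendix 4 makes the factor a CLASS variable in the MMRM and a STRATA variable in the Cox model, without limiting its levels. This stands. The natural reading is an ITT1 list carried over to ITT2. It does not supply the missing level, and the regression step in the same appendix has no CLASS statement, so its coding must come from the text.

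**4.6 already governs.** It is the dedicated multiplicity section and it states the stopping rule, so nominal in 5.1 may be only a loose label. That is the better reading, but the two sections still conflict as written.

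**Subgroups are outside the testing sequence.** True, and the <4 in the ITT2 subgroup may be a ≤ lost in PDF reading. The 1-2, 2-4, 1-4 list is unusable either way.

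**Leaving the factor out of the NfL model is a legitimate choice,** since TRICALS carries a progression rate. This stands in part, and no harm has been quantified. But by Appendix 3 that rate is the shortfall from 48 at screening divided by diagnostic delay, not the loss over the screening weeks.

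**Four Cox strata would be sparse.** Correct, with about 1.3 expected deaths. The fallback in 3.5 and 5.5 (partly stratified or unstratified models) should remain.

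**Conclusion.** The concern holds as four specification faults: a contradiction over the status of step 3, subgroup categories that cannot be fitted as stated, an unexplained omission of a randomization factor at step 5, and an unnamed level in the ITT2 models. The first two are wrong as written, the third is an inexpensive improvement, and the fourth is a clarification.

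A reader might infer that step 2 will simply repeat step 1 and so pass automatically. The documents do not support that. It would require someone to code >4 as missing, against the ITT2 definition, the baseline table, the ITT2 subgroup, the single exclusion in 5.5.1.1 and the sample code. It is a contingent risk touching at most about 33 planned subjects. The 4-12% figures for changed step 2 decisions also need an assumed zero or negative effect in those subjects; with an equal effect the figure is about 1% or less.

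The primary ITT1 analysis is unaffected.

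**What to change.** Amend the SAP wording before Part A is unblinded:

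1. In 5.1, delete nominal for the ITT2 CAFS comparison, so that 4.6 governs.
2. In 5.6, use the randomized levels <1, 1-2 and 3-4 for ITT1, and confirm that the ITT2 subgroup reads ≤4 versus >4.
3. Add the screening-decline factor to the NfL MMRM.
4. In 5.1, 5.5.1.1, 5.5.2 and 5.7, and in Part B/C SAP 5.2.1 and 5.4, state that the factor has four levels (<1, 1-2, 3-4, >4) whenever the model is run on ITT2. State the same for 5.5.1.2 and the imputation where they serve ITT2. Keep the sparse-strata fallback for the Cox model.

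The four-level variable already exists as a randomization stratum and a baseline-table row. The cost is two parameters (ITT1) or three (ITT2) in the NfL model, one extra parameter in the other ITT2 linear models, and up to two extra strata in the ITT2 Cox model. Alpha, sample size and data collection do not change.

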5.5.2. Analysis of Other Continuous Secondary Endpoints

The following secondary (continuous) endpoints will be analyzed for both the ITT1 and ITT2 analysis sets under the estimand framework described in Section 3.3.2, where an MMRM is used to implicitly impute missing data. The MMRM models will include fixed categorical effects of treatment (PTC857 or placebo), use of approved background therapy for ALS (Yes vs No), the amount of change in the subject's ALSFRS-R score during the Screening Period (<1, 1-2 or 3-4 points total loss), time of collection (nominal week at the visit as a categorical variable), as well as the continuous, fixed covariates of baseline endpoint variable (e.g., ALSFRS-R, ALSAQ-40), and The TRICALS risk profile. In addition, the following interaction terms will be included: Time by treatment, time by baseline value of endpoint, and TRICALS risk profile by time.

P-values for the treatment arm comparison at week 24, estimate of LSMEANS for the treatment differences (PTC857 – Placebo), and the two-sided 95% confidence intervals of the LSMEANS difference will be presented:

- Change from baseline in ALSFRS-R in the Intent-to-Treat 2 (ITT2) Analysis Set after 24 weeks of treatment.
- Quality of life as assessed by Amyotrophic Lateral Sclerosis Assessment Questionnaire (ALSAQ-40) after 24 weeks of treatment, for ITT1 and ITT2 analysis sets.
- Change from baseline in Modified Norris Scale total score, limbs score and bulbar score at Week 24, for ITT1 and ITT2 analysis sets.

• Change from baseline in slow vital capacity (SVC) as assessed by pulmonary function tests (PFTs) after 24 weeks of treatment for the ITT1 and ITT2 analysis sets.

To assess the change from baseline in plasma NfL after 24 weeks of treatment, log transformation of the plasma NfL results will be performed. A MMRM analysis will be performed, this analysis will include fixed categorical effects of treatment (PTC857 or placebo), use of approved background therapy for ALS (Yes vs No), time of collection (nominal week at the visit as a categorical variable), as well as the continuous, fixed covariates of baseline log plasma NfL, and The TRICALS risk profile. In addition, the following interaction terms will be included: Time by treatment, time by baseline log plasma NfL, and TRICALS risk profile by time. Geometric means and mean ratios to baseline, as well as the difference in geometric mean ratios for those in the PTC875 arm to those in the Placebo arm will be reported, together with 95% confidence intervals and p-values, for the ITT1 and ITT2 analysis sets. For this analysis values of plasma NfL that are BLQ will be set to half of LLOQ.

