1.5. Sample Size

For the primary efficacy endpoint, the combined assessment of ALSFRS-R and survival after 24 weeks of treatment, 307 subjects in the ITT1 Analysis Set (205 in the PTC857 group and 102 in the placebo group, based on a 2:1 randomization ratio) will provide approximately 85% power to detect a treatment difference of 2 points with a standard deviation of 5.3, based on a 2-sided 0.05 level Joint Rank Test, and assuming 24-week survival rates of 96.5% and 95% in the PTC857 and placebo groups, respectively. These assumptions took into consideration data from 2 clinical

studies in ALS which reached statistical significance for their primary endpoints that reported overall death rates of 0% and 5% (Edaravone (MCl-186) ALS 19 Study Writing Group 2017 and Paganoni, 2020) A standard deviation of 5.3 points for the ALSFRS-R score at Week 24, among treated subjects was reported for the edaravone study (Edaravone (MCl-186) ALS 19 Study Writing Group 2017).

Assuming approximately 10% of randomized subjects will not meet the ITT1 Analysis Set definition, then approximately 340 subjects will be randomized to ensure that 307 subjects are randomized into the ITT1 Analysis Set. Given that the primary analysis incorporates deaths as a combined endpoint, and a fully imputed analysis dataset is utilized in the analysis, additional enrollment and randomization to make up for discontinued subjects is not planned. This document clarifies a typographical error in the study protocol that incorrectly indicated a treatment difference of 2.5 points instead of 2 points, is of interest.

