4.6. Multiplicity

A fixed sequence testing procedure will be employed for selected efficacy endpoints. If the primary endpoint is statistically significant at a 2-sided 0.05 level, the secondary endpoints will then be tested sequentially in the order listed below, each at a 2-sided 0.05 alpha level. Testing within the specified sequence will stop if a null hypothesis in the sequence fails to be rejected.

- (1) Change from baseline in ALSFRS-R at Week 24 in the ITT1 analysis population
- (2) Change from baseline in ALSFRS-R at Week 24 in the ITT2 analysis population
- (3) Subject ranks based on the CAFS at Week 24 in the ITT2 analysis population
- (4) Change from baseline in total score of the Amyotrophic Lateral Sclerosis Assessment Questionnaire (ALSAQ-40) after 24 weeks of treatment, in the ITT1 analysis population
- (5) Change from baseline in log transformed plasma NfL, in the ITT1 analysis population There will be no interim analysis.

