5.3. Analysis of Continuous Long Term Extension Endpoints

The following continuous long term extension endpoints will be analyzed for both the ITT1 and ITT2 analysis sets using a similar model as described in Section 5.2.1, p-values for the treatment arm comparison, estimate of LSMEANS for the treatment differences (PTC857 – Placebo), and the two-sided 95% confidence intervals of the LSMEANS difference will be presented:

- Quality of life as assessed by Amyotrophic Lateral Sclerosis Assessment Questionnaire (ALSAQ-40) at 52 and 160 weeks.
- Change from baseline in Modified Norris Scale total score at 52 weeks.
- Change from baseline in slow vital capacity (SVC) as assessed by pulmonary function tests (PFTs) at 52 weeks.
- Change from baseline in neuropsychological function as assessed by the ALS CBS at 52 weeks.
- Change from baseline in log transformed NfL (plasma) at 52 weeks. Geometric means and mean ratios to baseline, as well as the difference in geometric mean ratio for those in the PTC875 arm to those in the Placebo arm will be reported, together with 95% confidence intervals and p-values.

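### The plasma NfL model, step 5 of the fixed testing sequence, omits the screening-decline stratum used in randomization, without a stated reason; the cost is a small loss of precision, not an inflated type I error

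*SAP*

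**What the plan says.** SAP (Part A) Section 1.1 names the first randomization factor as "Amount of change in ALSFRS-R score during the 8-week Screening Period by points total loss", with levels <1, 1-2, 3-4 and >4. Section 4.6 tests five secondary endpoints in fixed order after the primary, "each at a 2-sided 0.05 alpha level". The fifth and last is "Change from baseline in log transformed plasma NfL, in the ITT1 analysis population".

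For ALSAQ-40, the Norris scale and slow vital capacity, the Section 5.5.2 model includes "the amount of change in the subject's ALSFRS-R score during the Screening Period". The NfL paragraph in the same section does not refer back to that model. It writes out its own list: "A MMRM analysis will be performed, this analysis will include fixed categorical effects of treatment (PTC857 or placebo), use of approved background therapy for ALS", then visit, baseline log NfL, TRICALS, and the interactions of time with treatment, with baseline log NfL and with TRICALS. Screening decline is absent and no reason is given. The analysis is run in both ITT1 and ITT2.

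The between-arm summary is described in these words: "as well as the difference in geometric mean ratios for those in the PTC875 arm to those in the Placebo arm will be reported", with confidence intervals and p-values.

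The Parts B/C SAP, Section 5.3, analyses Week 52 NfL "using a similar model as described in Section 5.2.1". That section lists the screening-decline factor. Section 5.3 repeats the wording about a difference.

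**The concern.** A factor used to balance the arms at randomization normally belongs in the analysis model. Stratifying reduces the true sampling variability of the treatment contrast. If the model then ignores the stratum, the residual variance still contains the between-stratum part, so the reported standard error is larger than the true one. The test becomes conservative and the interval wider than it need be, to the extent that the stratum predicts NfL change.

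This is a formally tested endpoint, and its covariate list differs from the rest of the plan without explanation. What is at stake is some power and precision at the last step of the sequence, and an avoidable question about why this one model differs.

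The second matter is one of wording. A contrast of log-scale means back-transforms to a ratio with null value 1, whereas the text names a difference, which has null value 0.

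**Working it through.** **1. Is NfL the only main model without the stratum?** The Part A efficacy models, side by side:

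| Analysis (SAP Part A) | Screening decline in the model? |
|---|---|
| Primary CAFS ANCOVA (5.1) | Yes |
| ALSFRS-R MMRM (5.5.1.1) | Yes |
| ALSFRS-R ANCOVA after multiple imputation (5.5.1.2) | Yes |
| Control-based pattern mixture model (Appendix 4 code) | Yes |
| ALSAQ-40, Norris, slow vital capacity MMRMs (5.5.2) | Yes |
| Overall survival Cox model (5.7) | Yes, as a stratum |
| ALS-CBS (5.8, by reference to 5.5.1.1) | Yes |
| Plasma NfL MMRM (5.5.2) | **No** |

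Section 5.2 also leaves the factor out, but it is a labelled unstratified sensitivity analysis of the primary endpoint.

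**2. Does anything in the plan explain it?**
- Sections 3.5 and 5.5 allow a stratification factor to be dropped if sparse strata cause modeling problems. That is conditional. The sparsity described in 3.5 concerns background therapy, the factor that the NfL model keeps.
- TRICALS is not a substitute. Its progression term in Appendix 3 is (48 − screening ALSFRS-R) ÷ diagnostic delay, not the loss over the 8-week Screening Period.

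**3. Size.** The documents give no power, effect or SD for NfL, so there is no planned figure to reproduce. Inputs: 2-sided alpha 0.05 (Section 4.6) and 205 versus 102 subjects (Section 1.5, "307 subjects in the ITT1 Analysis Set (205 in the PTC857 group and 102 in the placebo group, based on a 2:1 randomization ratio"). Two assumptions are needed: R², the share of the remaining variance explained by the stratum, taken as 2% to 10%; and 80% power for the model that includes the stratum.

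With balance within strata, omitting the stratum inflates the model standard error by k = 1/√(1 − R²). Then:
- type I error = 2 × [1 − Φ(1.96 k)]
- power = Φ(1.960 + 0.842 − 1.96 k)

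For R² = 10%, k = 1/√0.90 = 1.054. Type I error = 2 × [1 − Φ(2.066)] = 3.9%, and power = Φ(0.736) = 76.9%.

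| R² (assumed) | CI width multiplier k | Type I error | Power (80% with stratum) |
|---|---|---|---|
| 2% | 1.010 | 4.8% | 79.4% |
| 5% | 1.026 | 4.4% | 78.5% |
| 10% | 1.054 | 3.9% | 76.9% |

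A simulation supports this. It used 307 subjects, 2:1 stratified blocks, assumed stratum shares of 35/40/25%, and 10,000 trials per setting. The Monte Carlo standard error for type I error is √(0.05 × 0.95/10,000) ≈ 0.2 points.

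| R² | Type I error, stratum omitted / included | Power, stratum omitted / included |
|---|---|---|
| 2% | 4.9% / 5.1% | 79.1% / 79.7% |
| 5% | 4.8% / 5.3% | 78.1% / 79.5% |
| 10% | 3.6% / 4.8% | 76.6% / 79.8% |

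**4. Difference or ratio.** Take a log-scale contrast of −0.1625. Its exponential is 0.85 whatever the placebo level. The arithmetic difference it implies is not fixed: placebo ratios to baseline of 0.90, 1.00 and 1.20 give PTC857 ratios of 0.765, 0.85 and 1.02, hence differences of −0.135, −0.150 and −0.180.

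**The case against.** The strongest case against is that little depends on this. Type I error is not inflated, and because NfL is last in the sequence no later test relies on it. TRICALS and its interaction with time are already in the model. Its progression term is not screening decline, but both measure pre-treatment progression, so the share left for the stratum may be near the low end of the range. All of that stands.

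It is also fair that copying the term from the other Section 5.5.2 models would do harm. Those models list only three levels, while the NfL model is also run in ITT2, which includes subjects who lost more than 4 points. They would have no level. The fix must allow for this.

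Three stronger readings are tempting but not supported:
- A reader might infer that the test's size is seriously distorted. At an assumed 10% share it is 3.9% by calculation and 3.6% by simulation; at smaller shares it is close to 5%.
- A reader might infer that the two SAPs contradict each other or the protocol. The Parts B/C text says similar, not identical, and that model must differ at least in its baseline covariate. Protocol Section 8.4.2 leaves other secondary endpoints to the SAP. The Parts B/C wording shows an inconsistency of approach, no more.
- A reader might infer that the NfL test has no defined scale, or that a difference could never have an interval. Section 4.6 fixes the test on log-transformed NfL, and an interval for a difference could be derived by the delta method, although none is specified. Loose wording is the likely cause.

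What the objection does not supply is a reason for the omission.

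**Conclusion.** The point holds as an unexplained omission with a modest, conservative effect. Plasma NfL is the only main Part A efficacy model without the screening-decline stratum, and no provision in the SAP accounts for it. For an assumed 2% to 10% share of the remaining variance, leaving it out widens the interval by about 1% to 5%, lowers type I error to between about 4.8% and 3.9%, and costs about 0.6 to 3 points of power from 80%. The low end is more likely, given TRICALS. These figures rest on the assumed share and the assumed 80%, neither of which is in the documents, and on near balance within strata. The validity of the test is not threatened. It is worth correcting because the endpoint is formally tested and the adjustment uses a factor that the trial already randomizes by. The ratio-versus-difference matter is a secondary wording correction.

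**What to change.** - **Model.** Before unblinding, add screening-period ALSFRS-R decline as a fixed categorical effect to the plasma NfL MMRM in SAP (Part A) Section 5.5.2. Use levels <1, 1-2 and 3-4 in ITT1, and add a >4 level in ITT2. If the omission is deliberate, state the reason.
- **If Part A is already unblinded.** Keep the written model as the tested one and report the adjusted model as a documented sensitivity analysis in the clinical study report.
- **Wording.** In Part A Section 5.5.2 and Parts B/C Section 5.3, define the between-arm summary as the ratio of geometric mean ratios, PTC857 over placebo, equal to exp(LS-mean difference), with the back-transformed 95% confidence interval and the log-scale p-value.

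The cost is one model term from data already collected and a few words of text. The sponsor has already used an erratum to correct covariate wording in Section 5.1, so a route exists. The only care needed is the >4 level in ITT2.
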